6.2 Baseline characteristics

6.2.1 Baseline values for primary efficacy variable components

Baseline values for the 7 components for primary efficacy variable will be summarized by treatment group and overall. The following variables will be summarized:

- TJC,
- SJC,
- PGA-PsA,
- PhGA-PsA,

- PtAAP,
- HAQ-DI,
- hs-CRP (mg/L).

For hs-CRP, SJC, and TJC the following rule will be applied: If Baseline value is missing, then take the most recent value (taken at previous unscheduled visit or at Screening); If value is still missing, the Baseline value will be considered missing. hs-CRP will be summarized using descriptive statistics and in classes (≥ 6 mg/L, < 6 mg/L).

Efficacy variables not listed above will not be presented in the Baseline characteristics section. They will be presented in by-visit tables in the context of the analysis of secondary and other efficacy variables.

To understand the study population during the different periods of the COVID-19 pandemic, the reporting of Baseline demographics will be repeated by COVID-19 pandemic period (pre-, during, and post- as determined by the Baseline visit date) on the SS.

6.2.2 Other baseline characteristics

The following variables will be summarized by treatment group and overall:

- Prior TNF α exposure (Intolerance to TNF α inhibitor, Inadequate response to 1 TNF α inhibitor, Inadequate response to 2 TNF α inhibitors) – IXRS randomization strata
- Prior TNF α exposure (Intolerance to TNF α inhibitor, Inadequate response to at least 1 TNF α inhibitor, Inadequate response to 2 prior or more TNF α inhibitors) – actual randomization strata
- % of BSA affected by PSO ($< 3\%$, $\geq 3\%$ to $\leq 10\%$, $> 10\%$)
- PASI score at Baseline (for subjects with PSO involving at least 3% of BSA at Baseline). This variable will be summarized as a continuous variable and in classes (< 10 , 10 to 20, > 20)
- BASDAI (< 4 , ≥ 4)
- Rheumatoid factor (positive, negative). A rheumatoid factor value < 30 IU/mL is defined as negative and a value ≥ 30 IU/mL is defined as positive. (Chemistry results / Proteins / Test=RF).
- Anti-cyclic citrullinated peptide (CCP) antibodies (Positive, Negative). Anti-CCP antibodies negative is a value < 20 U/mL and a value ≥ 20 U/mL is defined as positive.
- Nail psoriasis (yes, no)
- Dactylitis (“yes” if LDI score > 0 , “no” if LDI score = 0 or missing)
- Enthesitis based on LEI (“yes” if LEI score > 0 , “no” if LEI score = 0 or missing)
- Enthesitis based on SPARCC (“yes” if SPARCC > 0 , “no” if SPARCC = 0 or missing)
- Prior NSAID (yes, no)
- NSAID at Baseline (yes, no)
- Past cDMARDs therapy (yes, no)

- Prior cDMARDs (0, 1, ≥2) (see [Section 4.8](#))
- cDMARDs at Baseline (yes, no)
- HLA-B27 status (positive, negative)
- Methotrexate at Baseline (yes, no)
- Prior oral corticosteroids (yes, no)
- Oral corticosteroids at Baseline (yes, no)

The above data including extra-articular assessments will also be listed.

Efficacy variables not listed above will not be presented in the Baseline characteristics section. They will be presented in by-visit tables in the context of the analysis of secondary and other efficacy variables.

To understand the study population during the different periods of the COVID-19 pandemic, the reporting of Baseline demographics will be repeated by COVID-19 period (pre-, during, and post- as determined by the Baseline visit date) on the SS.

6.2.3 History of psoriatic arthritis and psoriasis

The following PsA history variables will be summarized overall and by treatment group:

- Time since first diagnosis of PsA (years). Time since first diagnosis will be summarized as a continuous variable and as categorical variables based on following categories: <1, 1 to <2, ≥2 years.
- Time since first diagnosis of PSO (years),

Time since first diagnosis of PsA/PSO (years) will be calculated as follows:

$$\frac{\text{Date of informed consent} - \text{Date of diagnosis}}{365.25}$$

- Age at first diagnosis of PsA (years),

Age at first diagnosis (years) of PsA will be calculated as:

$$\frac{\text{Date of diagnosis of PsA} - \text{Date of birth}}{365.25}$$

If the date of diagnosis is partial, it should be imputed to the most recent feasible date (ie, last day of the month if only day is missing, or the last day of the year if day and month are missing). Partial dates should not be imputed later than the subject's screening date. For subjects enrolled at German sites, only the year of birth may be entered into the eCRF for this study. For these subjects age will be calculated after imputing their date of birth to be on January 1st.

- PsA subtype (Polyarticular – symmetric arthritis, Oligoarticular – asymmetric arthritis, Distal interphalangeal joint predominant, Spondylitis predominant, Arthritis mutilans)

The data on history of psoriasis and psoriatic arthritis will be listed for all screened subjects.

6.3 Medical history and concomitant diseases

Medical history conditions are defined as conditions that have resolved prior to study entry.

Ongoing medical conditions are defined as conditions that are ongoing at the time of study entry.

Medical history and on-going medical conditions will be summarized on the SS by MedDRA System Organ Class (SOC) and Preferred Term (PT), by treatment and overall including the number and percentage of subjects with each condition. Psoriatic arthritis history will not be included in this table as it will be presented separately (Section 6.2.3). The denominator of the percentages will be the number of subjects in the population considered. The table summaries will be ordered alphabetically for SOC and in terms of decreasing frequency for PT within SOC in the BKZ treatment group. In the event of ties, PT will be ordered alphabetically.

Medical history and ongoing medical conditions will be listed by treatment and subject including the reported term, PT, and SOC for the RS. The start date (month and year only) and the end date (or ongoing if applicable) will be included in the listing. Partial dates will not be imputed. A glossary of all medical history conditions will be presented including the reported term, PT and SOC. Concomitant medical procedures will be listed on the RS.

6.4 Prior and concomitant medications

Prior medications include any medications that started prior to the start date of the first IMP administration.

Concomitant medications are medications taken at least one day in common with the study medication dosing period.

The IMP dosing period corresponding to the combined Double-Blind Treatment Period will be calculated as follows:

- The study medication dosing period start date is defined as the date of first dose.

The study medication dosing period stop date is defined as follows:

- For subjects who are ongoing at the time of the clinical data cut (not including subjects who are in SFU) use date of last clinical contact
- For subjects who died prior to last visit (not including those who died during SFU), use the minimum of the following:
 - Date of death
 - Date of last dose of any study medication + 28 days
- For subjects who complete the study as planned, the dosing period ends at the later of the following two dates:
 - Date of last administration of IMP + 28 days
 - The last scheduled visit date not including SFU
- For all other subjects, use the maximum of the following:
 - Date of last dose of any study medication + 28 days
 - Date of last visit (not including SFU)

In the case of missing data, the classification of medications as prior or concomitant will be performed as described in [Section 4.2.4](#). Imputations of missing data will be performed before calculation of relative study days.

The number and percentage of subjects taking prior medications and prior Anti-TNFs (excluding past psoriasis medications) will be summarized on the SS by treatment group, overall and by ATC class, presenting Anatomical Main Group (ATC Level 1), Therapeutical/Pharmacological Subgroup (ATC level 3), and preferred term (PT).

The table summary will be ordered alphabetically for the ATC class and in terms of decreasing frequency for PT within ATC class in the BKZ treatment group. In the event of ties, PT will be ordered alphabetically.

A by-subject listing of all prior medications and prior Anti-TNFs and concomitant medications on the SS as well as glossary of all medical medications will be provided.

6.5 Prohibited concomitant medications

Prohibited or restricted medications are defined in the protocol section 7.8.2.

Prohibited medications will be listed on SS.

7 MEASUREMENTS OF TREATMENT COMPLIANCE

Treatment compliance summaries will be performed based on the SS, by randomized treatment and for all subjects.

Due to the method of administration of the treatments, compliance will be examined in terms of completed injections. Treatment compliance will be calculated as:

$$\frac{\text{Total number of actual (completed) injections}}{\text{Total number of expected injections}} \times 100\%$$

The total number of expected injections is derived relative to when the subject finishes treatment.

If a subject completes treatment, 4 injections are expected (at Baseline, Week 4, Week 8 and Week 12).

If a subject discontinues early, then the number of expected injections is based on the time of early discontinuation relative to the dosing visits. This number will be calculated by determining the number of expected dosing visits prior to the date of early discontinuation. If the early discontinuation coincides with an expected dosing visit, this visit will be used to determine the number of expected injections.

A summary of percent treatment compliance categorized as <75% and ≥75% will be provided by treatment group, as well as a by-subject listing of treatment compliance.

8 EFFICACY ANALYSES

8.1 Statistical analysis of the primary efficacy variable

8.1.1 Derivation of ACR50 response

The ACR50 response at Week 16 is the primary efficacy variable.

This is a composite endpoint and represents at least 50% improvement from Baseline at Week 16 for each of the following:

- TJC (based on 68 joint count)
- SJC (based on 66 joint count)
- At least 3 of the 5 remaining core set measures:
 - PGA-PsA
 - PhGA-PsA
 - PtAAP
 - HAQ-DI
 - hs-CRP

Prior to deriving ACR50, the percent of change for each component will be calculated as:

$$\text{Percent improvement from Baseline} = 100 \times \frac{\text{Baseline Value} - \text{Week 16 value}}{\text{Baseline Value}}$$

As the ACR response is based on 7 different component scores, it is necessary to consider various data scenarios that could impact the calculation of ACR response. The rules described here are applicable in the context of the calculation of ACR response and may differ from the rules applied for calculating and summarizing the components, individually (some values may need to be imputed for component for component analysis but are not required here to evaluate the ACR response).

The following rules will be applied prior to invoking any imputation analysis at the variable level:

- If a subject has a component value that is equal to 0 at Baseline and the post-Baseline value is greater than or equal to 0, then the percentage of improvement for that component will be treated as 0 for purposes of ACR response calculations.
- If a subject has a component value that is missing at Baseline, then the percentage of improvement for that component will be treated as missing for purpose of ACR response calculations.

Observed data will be used to calculate ACR response where possible. In case of partial missing data where an observed response may be calculated, imputed data will not change the result.

To address possible missing data in ACR components, ACR50 will be derived as below:

- Positive response on ACR50
 - Improvement at Week 16 of at least 50% from baseline on SJC and TJC and at least 3 out of the 5 remaining ACR components (regardless of whether the two remaining components are missing or not)
- Negative response on ACR50

- No improvement at Week 16 of at least 50% from baseline on SJC (regardless of whether the remaining components are missing or not)
- No improvement at Week 16 of at least 50% from baseline on TJC (regardless of whether the remaining components are missing or not)
- No improvement for at least 3 out of the 5 ACR components (PGA-PsA, PhGA-PsA, PtAAP, HAQ-DI, hs-CRP) regardless of whether the remaining components are missing or not
- Missing ACR50 response
 - For all other situations that are not specified above.

For the OC analysis: if a given visit falls after the treatment discontinuation date, the endpoint at this visit and all subsequent visits (whether the data were observed or not) will be derived but reported as missing (Section 8.1.4.6).

For the MI analysis: if a given visit falls after the treatment discontinuation date, the endpoint at this visit and all subsequent visits (whether the data were observed or not) will be imputed. Responses falling after an IE (defined as treatment discontinuation due to AE or lack of efficacy for the modified composite estimand) will be set to nonresponse (Section 8.1.4.3).

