4.2.2.1 Non-responder imputation

For binary endpoints, the non-responder imputation (NRI) analysis, also described above as the primary composite estimand, will consider the following subjects as “non-responders” for the timepoint of interest:

- Subjects with missing data at the timepoint of interest. In the case of ACR50, nonresponse is imputed if ACR50 cannot be derived (ie, derived as “missing”) based on available ACR components. (Section 8.1.1).

- Subjects remaining in the study at the timepoint of interest but discontinuing study treatment before the timepoint of interest (data after IE).
- Subjects with missing Baseline value (for composite or non-composite binary variables based on change(s) from Baseline of continuous endpoint(s)).

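### The third negative-response rule for ACR50 omits the 50% threshold, so some non-responders who meet both joint-count criteria are classed as Missing; supportive analyses are exposed, the primary analysis is not

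*SAP*

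**What the plan says.** Section 8.1.1 defines the endpoint thus: "This is a composite endpoint and represents at least 50% improvement from Baseline at Week 16 for each of the following", and lists TJC, SJC and at least three of five further measures (PGA-PsA, PhGA-PsA, PtAAP, HAQ-DI, hs-CRP). It adds "Observed data will be used to calculate ACR response where possible".

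A three-way rule follows, introduced by "To address possible missing data in ACR components, ACR50 will be derived as below":

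- **Positive:** at least 50% improvement on SJC, on TJC and on at least three of the other five, whatever the status of the remaining two.
- **Negative:** any one of three branches: "No improvement at Week 16 of at least 50% from baseline on SJC"; "No improvement at Week 16 of at least 50% from baseline on TJC"; or "No improvement for at least 3 out of the 5 ACR components".
- **Missing:** "For all other situations that are not specified above".

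Under Section 4.2.2.1 the primary analysis treats a missing ACR50 as failure: "nonresponse is imputed if ACR50 cannot be derived (ie, derived as “missing”) based on available ACR components". In the observed-case analysis (Sections 4.2.1.3 and 8.1.4.6) missing stays missing. In the first tipping-point step (Sections 4.2.2.4 and 8.1.4.7) a missing ACR50 is set to non-response on BKZ and to response on placebo. Sections 8.2.1.5 and 8.3.1.2 derive ACR20 and ACR70 in the same way with 20% and 70%.

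**The concern.** Four of the five operative statements (the definition, the positive rule and the two joint-count negative rules) name the 50% threshold. The third negative branch does not. Taken at its words it covers only components that did not improve at all, so improvements above 0% but below 50% on the deciding components satisfy neither the positive nor the negative rule. The catch-all then labels the subject missing.

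A record with every component observed, or with enough observed to exclude response, should not be missing. A programmer who codes the rule as printed would produce a different data set from one who codes the definition, and the two would disagree wherever missing and non-response are handled differently. ACR20 and ACR70 inherit the problem, since the third branch contains no percentage to replace.

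**Working it through.** **1. The plan's own figure.** Inputs from Section 2.4.1: 26% vs 10%, 260 vs 130 subjects, two-sided 0.05, continuity-corrected chi-square. Recomputed power is 96.5% (97.6% without the correction), and OR = (0.26/0.74)/(0.10/0.90) = 3.16. The stated 96% and 3.16 reproduce.

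**2. A complete record.** SJC +60%, TJC +60%, two components +60%, three components +30%.
- Positive? No: two of five reach 50%, three are needed.
- Negative by SJC or TJC? No: both exceed 50%.
- Negative by the third branch as printed? No: none of the five failed to improve.
- Result as printed: missing. By the definition: non-responder.

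**3. A partial record.** SJC +60%, TJC +60%, three components observed at +30%, two missing. At most two of five can reach 50%, so response is already excluded. The printed rule again gives missing.

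**4. All patterns with both joint counts at 50% or more.** Code each of the five components H (50% or more), L (above 0% and below 50%) or N (no improvement). There are 3^5 = 243 complete patterns.
- Positive (three or more H): 10×4 + 5×2 + 1 = 51, leaving 243 − 51 = 192 non-responder patterns.
- Negative as printed (three or more N): 10×4 + 5×2 + 1 = 51.
- Missing as printed: 243 − 51 − 51 = 141.
- With the threshold added (three or more L or N): 192 negative, 0 missing.

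Allowing missing components gives 4^5 = 1,024 patterns. As printed, 106 are positive, 106 negative and 812 missing. With the threshold, 106 are positive, 512 negative and 406 missing. The positive set is the same, so under non-responder imputation no pattern changes status.

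**5. Observed-case analysis (illustration).** The documents give no affected share, so take a fraction f of non-responders in each arm as an assumption. The observed rate is p / [p + (1 − p)(1 − f)].

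| f, both arms | BKZ | Placebo | Difference | OR |
|---|---|---|---|---|
| 0 | 26.0% | 10.0% | 16.0 | 3.16 |
| 5% | 27.0% | 10.5% | 16.5 | 3.16 |
| 10% | 28.1% | 11.0% | 17.1 | 3.16 |
| 20% | 30.5% | 12.2% | 18.3 | 3.16 |

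Dropping f multiplies an arm's odds by 1/(1 − f), so OR = 3.162 × (1 − f placebo)/(1 − f BKZ). Equal shares leave it unchanged. Shares of 10% vs 5% give 3.34, and 20% vs 10% give 3.56.

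**6. Worst-case tipping step (illustration).** Start from 13/130 on placebo and 68/260 on BKZ, ignoring genuinely missing subjects. If m placebo non-responders are mislabelled, the placebo rate becomes (13 + m)/130, while BKZ is unchanged. For assumed m = 5 it is 18/130 = 13.8%; for m = 14 it is 27/130 = 20.8%. The unadjusted chi-square p-value (no continuity correction) is about 0.006 and 0.24 respectively.

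**The case against.** The strongest reply is that the section already settles these subjects. The definition puts 50% on every element, observed data take precedence where a response can be calculated, the three-way list is introduced as a device for missing components, and the joint-count branches show what the third one meant. On that reading the branch is elliptical and nobody with complete data would be called missing.

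This establishes the intent, but it does not repair the rule. Section 4.2.2.1 relies on an ACR50 derived as missing under Section 8.1.1, so the list is operative. The partial record in step 3 of the working is the case the list was written for, and the printed rule fails there too.

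Three stronger readings might be inferred, and the documents do not support them:

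- **Any non-responder with improvements of 1–49% is affected.** No. A subject below 50% on SJC or TJC is already negative. Only subjects who meet both joint-count criteria can fall into the gap.
- **These subjects drop out of the multiple-imputation analyses.** Not established. Imputation is done component by component, and the response is then derived for every subject and visit from the component values (Section 4.2.2.2, composite binary endpoints). Section 8.1.4.3 invokes Section 8.1.1 only for partial missing data. A missing label could arise there if the printed rule is applied literally, but the plan does not say that it will be.
- **The primary result is at risk.** No, because missing becomes non-response.

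**Conclusion.** The third negative rule is wrong as written, and the point is minor. Some subjects who meet both joint-count criteria but fail ACR50 are labelled missing, including subjects with complete data (141 of 192 non-responder patterns) and subjects whose partial data already exclude response. The primary analysis and the 96% power are untouched.

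Read literally, the rule removes true non-responders from the observed-case denominator. That raises the observed rate in any arm where it happens; the odds ratio moves only if the affected shares differ between arms. In the worst-case tipping step it converts such placebo subjects into responders, which works against BKZ and could by itself decide whether that step tips. The multiple-imputation derivations may be touched if they use the printed rule.

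How many subjects are involved cannot be derived from the documents. The fractions and counts in steps 5 and 6 are assumptions that show direction and scale, not estimates.

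**What to change.** Give the third negative branch in Section 8.1.1 the same Week 16, 50%-from-Baseline qualifier that the SJC and TJC branches have. In substance: less than 50% improvement on at least three of the five remaining components (PGA-PsA, PhGA-PsA, PtAAP, HAQ-DI, hs-CRP) is a negative response, whether or not the others are missing. State that 20% and 70% replace 50% in this branch for ACR20 and ACR70. One phrase changes before programming. It cannot alter any result under non-responder imputation, and it makes the observed-case, tipping-point and imputation derivations agree with the definition.

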8.1.1.1 Derivation of tender joint count (TJC) and swollen joint count (SJC)

Tender and swollen joints are assessed based on the 68 and 66 joints for tenderness and swelling, respectively. The 68/66 joints that are assessed are:

- Upper body (6) - bilateral temporomandibular, sternoclavicular, and acromioclavicular joints.
- Upper extremity (34) - bilateral shoulders, elbows, wrists (includes radiocarpal, carpal and carpometacarpal bones considered as a single unit), metacarpophalangeal (I, II, III, IV, and V), thumb interphalangeals, proximal interphalangeal (II, III, IV, and V), and distal interphalangeals (II, III, IV, and V).
- Lower extremity (28) - bilateral hips, knees, ankles, tarsi (includes subtalar, transverse tarsal, and tarsometatarsal considered as a single unit), metatarsophalangeals (I, II, III, IV, and V), great toe interphalangeals, and proximal interphalangeals (II, III, IV, and V).

The assessment on swelling exclude the hips.

Each of the joints can be graded as follows by the assessor:

- Permanently not assessable
- Temporarily not assessable
- Asymptomatic
- Tender only
- Swollen only
- Tender and swollen

Permanently non-evaluable joints will be considered missing for both tender and swollen joint counts at the visit at which the grading was recorded and all subsequent visits. The asymptomatic joints will be included in the joint count analysis with scores of 0.

For the statistical analysis, swelling and tenderness will be each graded on a 2-point scale as described below in [Table 8–1](#).

Table 8–1: Swelling and Tenderness grading

Present	Tenderness response (68)	Swelling response (66)
No (0)	Not tender	None
Yes (1)	Positive response to questioning (tender), spontaneous response elicited (tender and winced) or withdrawal by subject on examination (tender, winced, and withdrew)	Detectable synovial thickening with or without loss of bony contours, or bulging synovial proliferation with or without cystic characteristics

The joint graded by the assessor will then have its grade mapped as follows:

- The “Tender only” joints will correspond to a tenderness response of 1, and a swelling response of 0.
- The “Swollen only” joints will correspond to a swelling response of 1, and a tenderness response of 0.
- The “Tender and swollen” joints will correspond to a swelling and tenderness response of 1.

Dactylitic digits will be identified as follows and the joints will be counted as follows:

- Fingers 2-5: Swelling Distal Interphalangeal Joint x (side), Swelling Proximal Interphalangeal Joint x (side), Swelling Metacarpophalangeal Joint x (side) – if they are in any of the gradings ‘swollen-only’ or ‘tender and swelling’ or ‘injected’ then only 1 finger will be added to the swollen joint count
- Toes 1-5: Swelling Interphalangeal Joint x (side), Swelling Metatarsophalangeal Joint x (side) – if they were in any of gradings ‘swollen’ or ‘tender and swollen’ or ‘injected’ then only 1 toe will be added to the swollen joint count

The tender joint count (TJC) and swollen joint count (SJC) are weighted joint counts. If there are missing observations in the tender or swollen joint assessments (TJ and SJ, respectively), then the remaining observations will be assessed and weighted by the number of the assessed joints (AJ) as shown below:

$$TJC = n \times \frac{\sum_{i=1}^n TJ}{\sum_{i=1}^n AJ}$$

$$SJC = n \times \frac{\sum_{i=1}^n SJ}{\sum_{i=1}^n AJ}$$

Where n represents the number of total joints.

However, if a joint is missing at Baseline, then that joint will be set to missing throughout the study. If more than 50% of the planned tender joint assessments (ie, more than 34) or 50% of the

planned swollen joint assessments (ie, more than 33) are missing at any post-Baseline visit, then no imputation will be done and the total TJC or SJC will be set to missing for that visit.

